#### **4.3. Subject Disposition**

Individual patient disposition data will be listed.

Frequency counts will be tabulated for disposition data and will include the following:

- Number of patients enrolled [Part 1 only],
- Number of patients randomized [Part 2 only],
- Number (%) of patients completing the study [Part 1 only],
- Number (%) of patients completing the double-blind treatment period [Part 2 only]
  - A patient is said to have completed the double-blind treatment period if the patient completed up to and including the Day 190 visit.
- Number (%) of patients entered into the open-label period [Part 2 only]
- Number (%) of patients completing the open-label treatment period [Part 2 only]
  - A patient is said to have completed the open-label treatment period if the patient completed up to and including the Day 337 visit.
- Number (%) of patients that rollover to the extension study, A083-04
  - Patients that rollover to the extension study consist only of patients participating in Part 2 of this study who complete both the double-blind treatment period AND the open-label treatment period who will not have the Day 393/EOS visit. These patients' final study visit will be the Day 358/ET visit.
- Number (%) of patients that do not rollover to the extension study A083-04
  - Patients that do not rollover to the extension study will have both the Day 358/ET and Day 393/EOS visits completed.

- Number (%) of patients discontinuing from the study prior to completing both the double-blind period and the open label period [Part 2 only]
  - Number (%) of patients that discontinued during the double-blind period
  - Number (%) of patients that discontinued during the open-label period
  - Number (%) of patients for primary reason for discontinuation will also be provided [provided there is at least one patient who discontinued].

Summaries will be provided by treatment and overall for each study part (Part 1 and Part 2).

## 4.4. Demographic and Baseline Characteristics

### 4.4.1. Demographics

Individual demographic data will be listed.

Descriptive statistics (N, mean, SD, median, minimum and maximum) will be provided for continuous demographic variables (age, weight, height, and BMI) and frequency counts will be tabulated for categorical demographic variables (gender, race, ethnicity) by treatment and overall for each study part (Part 1 and Part 2). Age will be calculated based on birth date and informed consent date.

### 4.4.2. Baseline Characteristics

Baseline characteristics of the patient population consist of selected items from the FSHD disease history, MRI, MRC-MMT, and functional test data. Such data includes the following:

- FSHD disease diagnosis
  - The disease diagnosis values are either FSHD1 or FSHD2
- D4Z4 fragment size (kilobases)
  - The D4Z4 fragment sizes will be grouped into the following categories:  $\leq 18$  kb; 19-28 kb;  $> 28$  kb (These categories roughly correspond with categories based on number of D4Z4 repeats.)
- Scapular fixation surgery
  - This is a categorical variable whose possible values are “Right”, “Left”, “Both”, or “No History”.
  - This is derived off of the responses to the question “Did the patient have history of scapular fixation surgery” (responses are “Yes” or “No”) and if “Yes”, then the choice of either “Right”, “Left”, or “Both” would be selected.
  - A value of “No History” would be the case where the answer to the question “Did the patient have history of scapular fixation surgery” is “No”.
- Wears any lower limb orthotics/braces
  - This is a categorical variable whose values are “Right”, “Left”, “Both”, or “Does not wear”.

- This is derived off of the responses to the question “Does the patient currently wear any lower limb orthotics/braces” (responses are “Yes” or “No”) and if “Yes”, then the choice of either “Right”, “Left”, or “Both” would be selected.
  - A value of “Does not wear” would be the case where the answer to the question “Does the patient currently wear any lower limb orthotics/braces?” is “No”.
- Walking device use
  - Values are “Yes” or “No”
- First degree relatives with FSHD
  - Values are “Yes” or “No”
- Exercise program
  - This is a categorical variable whose values are “Aerobic 1-2 times per week”, “Aerobic 3-4 times per week”, “Aerobic 5+ times per week”, “Resistance training 1-2 times per week”, “Resistance training 3-4 times per week”, “Resistance training 5+ times per week”, “Both aerobic and resistance training 1-2 times per week”, “Both aerobic and resistance training 3-4 times per week”, “Both aerobic and resistance training 5+ times per week”, and “No exercise program”
  - This is derived off of the responses to the question “Does the patient have a regular exercise program” (responses are “Yes” or “No”) and if “Yes”, then the choices of how many times a week overall (1-2, 3-4, or 5+) and the type of exercise (Aerobic, Resistance training, or Both) would be selected.
- Age at onset of symptoms (years)
- Age at diagnosis (years)
- Duration since onset of symptoms (years)
  - Duration since onset of symptoms = Age (years) – Age at onset of symptoms (years)
- Duration since diagnosis (years)
  - Duration since diagnosis = Age (years) – Age at diagnosis (years)
- Total muscle volume (mm^3)
  - See [Section 4.7.1](#) for definition.
- Total muscle mass (g)
  - See [Section 4.7.1](#) for definition.
- Calculated contractile muscle volume (mm^3)
  - See [Section 4.7.1](#) for definition.
- Calculated contractile muscle mass (g)
  - See [Section 4.7.1](#) for definition.

- Fat fraction (%)
- 6-minute walk distance (m)
- Time to complete 10 meter walk/run (s)
- PUL composite time (s)
- MRC-MMT grade category

**Part 1**

- MRC-MMT grades will be grouped into the following categories: [3 to 4-], [4 to 4+], [5- to 5]
- For unilateral dose cohorts, summaries to be provided will be the side treated and will either be that of elbow flexion (for those receiving study drug in the BB muscle), ankle dorsiflexion (for those receiving study drug in the TA muscle), or knee extension (for those receiving study drug in the TA muscle).
- For those receiving study drug bilaterally, each side will be summarized
  - Elbow flexion (for those receiving study drug in the BB muscle)
  - Ankle dorsiflexion (for those receiving study drug in the TA muscle)
  - Knee extension (for those receiving study drug in the TA muscle).

**Part 2**

- MRC-MMT grade classification: [3 to 4-] and [4 to 4+].
- MRC-MMT grades will also be summarized (frequency with percents) by the weakest grade for each of the following:
  - Elbow flexion (BB patients) – possible values are 3, 3+, 4-, 4, 4+
  - Ankle dorsiflexion (TA patients) – possible values are 3, 3+, 4-, 4, 4+
  - Knee extension (TA patients) – possible values are 2-, 2, 2+, 3-, 3, 3+, 4-, 4, 4+, 5-, 5.
- MRC-MMT SCORE which represents the conversion of the MRC-MMT grade to the decimal version as follows: 5 = 5.0, 5- = 4.67, 4+ = 4.33, 4 = 4.0, 4- = 3.67, 3+ = 3.33, 3 = 3.0, 3- = 2.67, 2+ = 2.33, 2 = 2.0, 2- = 1.67, 1+ = 1.33, 1 = 1.0.
  - For unilateral dose cohorts, summaries to be provided will be for the side treated and will either be that of elbow flexion (for those receiving study drug in the BB muscle) or ankle dorsiflexion (for those receiving study drug in the TA muscle).
  - For bilateral dose cohorts, this will be determined for each side (left and right) and then averaged. Only the “average” will be presented in the summary table.
- Dose of ACE-083 expressed as (mg/g calculated total muscle mass)
- Dose of ACE-083 expressed as (mg/g calculated contractile muscle mass)

The table below outlines how to derive the dose of ACE-083 expressed as either mg/g total muscle, or mg/g contractile muscle:

	Dose of ACE-083 Expressed as	
	mg/g Calculated Total Muscle Mass	mg/g Calculated Contractile Muscle Mass
Unilateral Cohorts	Dose injected (mg) / (Baseline CCMV {mm3}* [1.06/1000] + Baseline CIMFV {mm3} * [0.9/1000])	Dose injected (mg) / (Baseline CCMV {mm3}* [1.06/1000])
Bilateral Cohorts	
Step 1: For each side (right and left), compute the following: Dose injected (mg) / (Baseline CCMV {mm3}* [1.06/1000] + Baseline CIMFV {mm3} * [0.9/1000])
 
Step 2: Compute average of the Dose of ACE-083 expressed as mg/g total muscle for each side using the information obtained from Step 1.
	
Step 1: For each side (right and left), compute the following: Dose injected (mg) / (Baseline CCMV {mm3}* [1.06/1000])
 
Step 2: Compute average of the Dose of ACE-083 expressed as mg/g contractile muscle for each side using the information obtained from Step 1.

CCMV = Calculated contractile muscle volume; CIMFV = Calculated intramuscular fat volume

Note: For unilateral cohorts, this will be determined only for the side that is treated.

This data will be summarized using appropriate descriptive statistics.

## 4.5. Prior and Concomitant Medications/Therapy

Prior and concomitant medications recorded during the study will be listed. These will be coded with the WHO Drug Dictionary (Version 2016-09).

Medications will be assigned as prior or concomitant based on the following rules:

- If both the start and stop date exist and are before the first dose date of study drug, the medication will be classified as a prior medication.
- If the start date is on or after the first dose date of study drug, the medication will be classified as a concomitant medication.
- If the start date is before the first dose date of study drug and the stop date is after the first dose date of study drug or the medication is ongoing, the medication will be classified as prior and concomitant.
- If the start date is missing and the stop date is before the first dose of study drug, the medication will be classified as prior.
- If the start date is missing and the stop date is after the first dose of study drug or the medication is ongoing, the medication will be classified as concomitant.
- If the start and stop dates are missing, the medication will be classified as concomitant.

## 4.6. Study Drug Exposure

### 4.6.1. Extent of Exposure

A listing of individual patient dosing data will be provided.

Study drug exposure will be summarized descriptively by cohort (Part 1) and by treatment group for each muscle (Part 2) for the safety population. Such summaries will include the total number

of treatment cycles, the number and percentage of patients with dose delay and reduction. If no patients experience dose delay and reduction, then no such summaries will be provided.

The total number of cycles will be summarized by presenting the number and percentage of patients in each category. Categories refer to the total number of treatment cycles. For Part 1, the possible values of the total number of treatment cycles are: “1”, “2”, “3”, “4”, and “5”. For Part 2 (double-blind period), the possible values of the total number of treatment cycles over the course of the double-blind treatment period is: “1”, “2”, “3”, “4”, “5”, “6”, “7”, “8”, or “9”. For Part 2 (open-label extension), the possible values of the total number of treatment cycles over the course of the open-label extension is: “1”, “2”, “3”, “4”, “5”, “6”, “7”, or “8”.

The total study drug exposure in weeks will also be summarized and will be derived according to the following formula: Exposure (weeks) = [(Last dose date – First dose date) +21] / 7.

For Part 1, summaries of the total study drug exposure in weeks will be provided by cohort using descriptive statistics. The summary table will include a pooled summary across cohorts within each muscle treated.

For Part 2, summaries of the total study drug exposure in weeks will be provided by treatment group for each muscle treated.

## 4.7. Efficacy Data

### 4.7.1. Variables

#### 4.7.1.1. MRI

MRI variables consist of the following:

Variable	Unit	Formula for derivation or SAS variable name/expression from SDTM FA
Total muscle volume (TMV)	mm 	TMV = Contractile muscle tissue volume (SAS variable FASTRESN in SDTM FA where FATESTCD = “MVOL”) + Intramuscular fat volume (SAS variable FASTRESN in SDTM FA where FATESTCD=“IFATVOL”)
Intramuscular fat volume (IMFV)	mm 	SAS variable FASTRESN in SDTM FA where FATESTCD=“IFATVOL”
Contractile muscle volume (CMV)	mm 	SAS variable FASTRESN in SDTM FA where FATESTCD=“MVOL”
Fat fraction (FF)	%	SAS variable FASTRESN in SDTM FA where FATESTCD=“FATF”
Contractile muscle fraction (CMF)	%	CMF = 100 – FF
Calculated contractile muscle volume (CCMV)	mm 	CCMV = TMV * CMF/100
Calculated intramuscular fat volume (CIMFV)	mm 	CIMFV = TMV * FF/100
Contractile muscle mass (CMM)	g	CMM = CMV * 1.06/1000

Variable	Unit	Formula for derivation or SAS variable name/expression from SDTM FA
Intramuscular fat mass (IMFM)	g	IMFM = IMFV * 0.9/1000
Total muscle mass (TMM)	g	TMM = CMM + IMFM
Calculated contractile muscle mass (CCMM)	g	CCMM = CCMV * 1.06/1000
Calculated intramuscular fat mass (CIMFM)	g	CIMFM = CIMFV * 0.9/1000
Calculated total muscle mass (CTMM)	g	CTMM = CCMM + CIMFM

#### 4.7.1.2. Muscle Strength

Muscle strength variables consist of the following:

- For cohorts where treatment is administered unilaterally
  - Ankle dorsiflexion (maximum voluntary isometric contraction [MVIC]) for the treated TA muscle [TA cohorts]
    - a. MVIC = maximum force (from 3 measurements) from the hand-held dynamometer.
    - b. The treated TA muscle can be either the right or left side. The treated and untreated sides will remain the same for the individual patient throughout the study.
  - Elbow flexion (MVIC) for the treated BB muscle [BB cohorts]
    - a. MVIC = maximum force (from 3 measurements) from the hand-held dynamometer.
    - b. The treated BB muscle can be either the left or right side. The treated and untreated sides will remain the same for the individual patient throughout the study.
- For cohorts where treatment is administered bilaterally
  - Maximum (of 3 measurements) right ankle dorsiflexion (MVIC) [TA cohorts]
  - Maximum (of 3 measurements) left ankle dorsiflexion (MVIC) [TA cohorts]
  - Maximum (of 3 measurements) right elbow flexion (MVIC) [BB cohorts]
  - Maximum (of 3 measurements) left elbow flexion (MVIC) [BB cohorts]

For each of the MRI and muscle strength variables listed above, the absolute and percent change from baseline will be determined for each side (“Treated”, “Untreated”, and “Treated – Untreated” sides for unilateral dose cohorts; “Left”, and “Right” sides for bilateral dose cohorts) and time. In addition, for bilateral dose cohorts, the average of the absolute change from baseline as well as the average of the percent change from baseline for the left and right sides will also be determined.

#### 4.7.1.3. Motor Function

##### 4.7.1.3.1. Lower Leg Function Assessments

###### 10-Meter Walk/Run Test

- Time to complete 10-meter walk/run (seconds)

###### 4-Stair Climb

- Ascending

- Time to ascending stairs (sec.)

- Number and percentage of patients belonging to the following grades:

1. Unable to climb 4 standard stairs
2. Climbs 4 standard stairs “marking time” (climbs one foot at a time, with both feet on a step before moving to next step), uses both arms on one or both handrails
3. Climbs 4 standard stairs “marking time” (climbs one foot at a time, with both feet on a step before moving to next step), using one arm on one handrail
4. Climbs 4 standard stairs “marking time” (climbs one foot at a time, with both feet on a step before moving to next step), not needing handrail
5. Climbs 4 standard stairs alternating feet, needs handrail for support
6. Climbs 4 standard stairs alternating feet, not needing handrail support
7. Not Done

- Descending

- Time to descending stairs (sec.)

- Number and percentage of patients belonging to the following grades:

1. Unable to descend 4 standard stairs
2. Descends 4 standard stairs “marking time” (climbs one foot at a time, with both feet on a step before moving to next step), uses both arms on one or both handrails
3. Descends 4 standard stairs “marking time” (climbs one foot at a time, with both feet on a step before moving to next step), using one arm on one handrail
4. Descends 4 standard stairs “marking time” (climbs one foot at a time, with both feet on a step before moving to next step), not needing handrail
5. Descends 4 standard stairs alternating feet, needs handrail for support
6. Descends 4 standard stairs alternating feet, not needing handrail support
7. Not Done

- **6-Minute Walk Test**
  - Cumulative distance traveled at 6 minutes (meters)
  - Cumulative distance traveled at 1 minute (meters)
  - Cumulative distance traveled at 2 minutes (meters)
  - Cumulative distance traveled at 3 minutes (meters)
  - Cumulative distance traveled at 4 minutes (meters)
  - Cumulative distance traveled at 5 minutes (meters)
- Gait Assessments
  - General measures: Ambulation distance (meters), Ambulation time (ms), Ambulation velocity (cm/s), Mean normalized velocity (Leg lengths/s), Number of steps, Cadence (steps/min.), Step time differential (ms), Step length differential (m), Cycle time differential (ms), Forward lean (deg.), Sway (m), Left step time (ms), Left Cycle Time (ms), Left Step Length (m), Left stride length (m), Left base width (m), Left single support (% gait cycle), Left initial double support (% gait cycle), Left terminal double support (% gait cycle), Left total double support (% gait cycle), Left swing (% gait cycle), Left stance (% gait cycle), Left step extremity ratio (ratio), Right step time (ms), Right Cycle Time (ms), Right Step Length (m), Right stride length (m), Right base width (m), Right single support (% gait cycle), Right initial double support (% gait cycle), Right terminal double support (% gait cycle), Right total double support (% gait cycle), Right swing (% gait cycle), Right stance (% gait cycle), Right step extremity ratio (ratio)
  - Initial measures: Initial left hip flexion (deg.), initial left knee flexion (deg.), initial left ankle dorsiflexion (deg.), initial left clearance (cm), Initial right hip flexion (deg.), initial right knee flexion (deg.), initial right ankle dorsiflexion (deg.), initial right clearance (cm)
  - Peak measures: Peak left hip min (deg.), Peak left hip max (deg.), Peak left knee min (deg.), Peak left knee max (deg.), Peak left ankle dorsiflexion min (deg.), Peak left ankle dorsiflexion max (deg.), Peak left clearance max (cm.), Peak right hip min (deg.), Peak right hip max (deg.), Peak right knee min (deg.), Peak right knee max (deg.), Peak right ankle dorsiflexion min (deg.), Peak right ankle dorsiflexion max (deg.), Peak right clearance max (cm.)
  - Average measures: Average left hip min (deg.), Average left hip max (deg.), Average left knee min (deg.), Average left knee max (deg.), Average left ankle dorsiflexion min (deg.), Average left ankle dorsiflexion max (deg.), Average left clearance max (cm.), Average right hip min (deg.), Average right hip max (deg.), Average right knee min (deg.), Average right knee max (deg.), Average right ankle dorsiflexion min (deg.), Average right ankle dorsiflexion max (deg.), Average right clearance max (cm.)
- 100-meter timed test (patients receiving ACE-083 in the TA muscle during the Part 2 open-label phase)

- Time to complete 100-meters (sec.)

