#### **Motor Function (Lower Leg): 4-Stair Climb (TA Muscle Group)**

Individual data will be listed.

Descriptive statistics of raw data as well as absolute and percent changes from baseline will be provided by cohort (for Part 1) and by treatment group (for Part 2) for time to ascend as well as time to descend data.

An ANCOVA model will be fitted in order to assess the effect of ACE-083 on the Day 190 percent change in the time to ascend 4-stairs from baseline data. Covariates to be included in the model are TREATMENT, MRC-MMT GRADE CATEGORY, and BASELINE where BASELINE represents the baseline time to ascend 4-stairs, and each of the other covariates are defined the same as what was done for the primary efficacy analysis.

The effect of ACE-083 on the Day 190 percent change in the time to ascend 4-stairs from baseline versus placebo will be estimated using the ANCOVA model described above and tested using a 0.1 significance level (2-sided). The least-squares mean estimate along with the corresponding 90% confidence interval will be provided. In addition, the 95% confidence

interval will also be provided as well as a bar chart of the least squares mean estimates ( $\pm$  SEM) for each of the treatment groups.

An ANCOVA model will be fitted in order to assess the effect of ACE-083 on the Day 190 percent change in the time to descend 4-stairs from baseline data. An unstructured covariance structure will be used to model the within-patient covariance across visits. Other covariance structures will be considered if the unstructured covariance fails. Covariates to be included in the model are TREATMENT, MRC-MMT GRADE CATEGORY, and BASELINE where BASELINE represents the baseline time to descend 4-stairs, and each of the other covariates are defined the same as what was done for the primary efficacy analysis.

The effect of ACE-083 on the Day 190 percent change in the time to descend 4-stairs from baseline versus placebo will be estimated using the ANCOVA model described above and tested using a 0.1 significance level (2-sided). The least-squares mean estimate along with the corresponding 90% confidence interval will be provided. In addition, the 95% confidence interval will also be provided as well as a bar chart of the least squares mean estimates ( $\pm$  SEM) for each of the treatment groups.

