A mixed model repeated measures (MMRM) analysis will be performed to assess the sensitivity to the ANCOVA analyses described above. The covariates to be included consist of all of the covariates described above for the ANCOVA with the addition of the following additional covariates: VISIT where VISIT represents the scheduled visit day post first dose of MRI assessment and TREATMENT\*VISIT.

For both the ANCOVA and MMRM analyses, multiple imputations will be performed for missing data. Twenty imputations will be performed. The seed to be used is specified in [Section 6](#). The assumption of the missing data mechanism will be missing at random (MAR) unless the data suggest otherwise. The missing data pattern (monotone or arbitrary) will also be evaluated and the regression method for imputing missing data will be utilized for each scheduled timepoint with missing data. Covariates to be included when imputing missing data include: MRC-MMT GRADE CATEGORY, TREATMENT, BASELINE, and 4-stair ascend (or descend) time percent change data at scheduled timepoints prior to the timepoint at which 4-stair ascend (or descend) time percent change is being imputed.

The table below illustrates the covariates that should be used for imputing missing data for selected timepoints:

Data to be Imputed	Covariates to use in Multiple Imputation Regression Model
Baseline time to ascend (or descend) 4 stairs	MRC-MMT GRADE CATEGORY, TREATMENT
Day 22 percent change in time to ascend (or descend) 4 stairs from baseline	MRC-MMT GRADE CATEGORY, TREATMENT, BASELINE
Day 43 percent change in time to ascend (or descend) 4 stairs from baseline	MRC-MMT GRADE CATEGORY, TREATMENT, BASELINE, Day 22 4-stair climb ascend (or descend) time percent change
Day 190 Percent change in time to ascend (or descend) 4 stairs from baseline	MRC-MMT GRADE CATEGORY, TREATMENT, BASELINE, Days 22, 43, 64, 85, 106, 148, and 169 4-stair climb ascend (or descend) time percent change from baseline

Analysis findings will be presented for Day 190 percent change data where missing data is not imputed (observed data) as well as for Day 190 percent change data where multiple imputations are performed for missing data to assess the impact of the missing data on the observed study data. The analyses where multiple imputations are performed are considered to be primary.

The Per Protocol Set will be used for the primary analysis. The analyses described above will also be repeated for the Full Analysis Set.

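### In the Part 2 4-stair climb analyses, inability has no value of its own, so becoming unable appears to be imputed as a finite time instead of counting as the worst outcome

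*SAP*

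**What the plan says.** SAP 4.7.1.3.1 collects two things for the 4-stair climb: a time, and an ability grade from 1 to 7. Grade 1 is "Unable to climb 4 standard stairs" for ascent and "Unable to descend 4 standard stairs" for descent. Grade 7 is a separate category for a test not done. The only use given for the grades is "Number and percentage of patients belonging to the following grades".

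The tests are on time. SAP 4.7.2.2 (4-Stair Climb, TA Muscle Group) fits an ANCOVA to the Day 190 "percent change in the time to ascend 4-stairs from baseline data", and does the same for descent, at a 2-sided 0.10 level.

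For gaps in the times, "For both the ANCOVA and MMRM analyses, multiple imputations will be performed for missing data" and "The assumption of the missing data mechanism will be missing at random (MAR) unless the data suggest otherwise". The imputation covariates are MRC-MMT category, treatment, baseline time and percent change at earlier visits. The ability grade is not among them. The imputation table includes a row for "Baseline time to ascend (or descend) 4 stairs". An observed-data version is also reported, but "The analyses where multiple imputations are performed are considered to be primary".

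SAP 4.7.2.5 adds a criterion of 10% change in ascent time, compared by Fisher's exact test, with no rule for an unable patient.

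**The concern.** A patient who can no longer climb four stairs has had about the worst result this test can give. The SAP recognises that result in the grades, yet the time endpoint has no place for it. If the time is simply blank, the imputation model supplies one, based on patients who can still climb. The value is absent because of the outcome itself, which is where missing at random is least credible.

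The distortion depends on which arm loses function. Losses on placebo would shrink a real benefit. Losses on ACE-083 would make the drug look better. With 12 to 14 patients per arm, each patient is 7% to 8% of the arm (1/14 = 7.1%, 1/12 = 8.3%).

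No other planned analysis repairs this. The observed-data version leaves the patient out, and the MMRM uses the same imputations. The qualifier on missing at random has no trigger and no alternative. By contrast, SAP 4.7.1.3.2 scores inability as 0, the lowest value, for the shoulder items of the upper-limb test.

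**Working it through.** **1. The plan's own figure.** No power, SD or expected number unable is stated for stair time. The only sizing figures are in SAP 4.1.1: a 10-point difference, SD 9%, 12 per arm, 2-sided 0.10, power 83%, for total muscle volume. The noncentrality is 10 / (9 × √(1/12 + 1/12)) = 10 / 3.674 = 2.72 on 22 degrees of freedom, which gives 83.9% power by the t-test. The stated figure reproduces. The illustration below borrows this scale for stair time; that is an assumption.

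**2. What happens to a grade 1 patient.**
- Grade recorded: yes, and counted.
- Substitute time, cap or rank: none in either document. The rule in SAP 4.1.5 for results recorded as greater than X is written for descriptive statistics and needs a recorded cap.
- Inferred result: the time is missing and is imputed at Day 190 from MRC-MMT category, treatment, baseline and the listed visits from Day 22 to Day 169.

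**3. Illustration of direction and size (all inputs assumed).** There are 12 patients per arm. The earlier-visit change x has SD 9. The Day 190 change is y = 0.7x + error − 10 for ACE-083, where the error has SD 9 × √(1 − 0.7²). Earlier values on ACE-083 are then lowered by 7. The k slowest patients in one arm at Day 190 are unable. Their times are imputed 20 times by regression on treatment and the earlier visit. There were 1,500 runs per row, with a simulation error of about 0.1 on each estimate (3.674/√1500). A negative estimate favours ACE-083.

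| Unable at Day 190 | Estimate if all had times | Estimate after imputation | Shift | Rejects: t-test on observed times | Rejects: worst-rank test |
|---|---|---|---|---|---|
| none | −10.1 | −10.1 | 0 | 83.7% | 81.2% |
| 1 placebo | −10.0 | −9.3 | +0.7 | 75.8% | 82.2% |
| 2 placebo | −9.9 | −8.5 | +1.4 | 62.4% | 81.6% |
| 3 placebo | −10.0 | −8.1 | +1.9 | 54.4% | 83.7% |
| 1 ACE-083 | −9.9 | −10.6 | −0.7 | 91.9% | 75.6% |
| 2 ACE-083 | −10.1 | −11.5 | −1.4 | 97.1% | 65.4% |
| 3 ACE-083 | −10.1 | −12.0 | −2.0 | 96.8% | 32.9% |

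Measured against the nominal −10, the shifts run from 0.6 to 2.0 points, always in favour of the arm that lost ability. With no true effect on time and 1, 2 or 3 placebo patients unable, the imputed estimate is 0.5, 1.4 or 1.9 points in favour of placebo.

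**4. Limits of the illustration.** It uses one earlier visit, where the SAP lists several; better prediction would reduce the shift. Rejection rates were computed for the observed-data t-test and an unstratified rank test, not for the imputed ANCOVA. The shift is measured against the finite time a patient would have had, so it does not price inability as an outcome in itself.

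**The case against.** The strongest reply is that the SAP never says an unable patient's time is missing, and that test procedures sit in the Study Manual (Protocol 12.2), which is not available here. That is fair: the step is an inference. It still leaves the SAP without a stated value for a result it expects to record.

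Second, few such patients may exist. Protocol 8.2, exclusion 2, bars impairment that in the investigator's judgement would limit completing the functional assessments. Part 2 TA entry also needs a 6-minute walk of at least 150 m without a brace and dorsiflexion grade 3 to 4+ on both sides. The disease is described as slowly progressive, and the blinded period is 6 months. This limits the likely size but does not rule out loss during treatment. The SAP also allows for TA patients with knee extension as weak as grade 2-.

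Third, imputation conditions on the patient's own earlier times, so a slowing patient draws a slow value. That is true, and it is why the shifts above are modest. Inability also remains visible in the grade counts, though these are not tested.

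Some stronger readings do not stand:
- A reader might infer that patients unable at entry will be given invented baseline times. SAP 4.1.4 averages up to three pre-dose values, so all would have to be missing, and exclusion 2 makes that unlikely. It is possible, not expected.
- A reader might extend the point to the 10-meter walk/run. SAP 4.7.1.3.1 lists only a time for that test and shows no unable category.
- A reader might size the bias by coding 2 of 14 placebo patients as −100% speed: 2/14 × 100 = 14.3 points. The counts are assumed and the scale is speed, while the endpoint is percent change in time. It is not a bias estimate.
- A reader might prefer absolute change in speed, with 0 for unable. Going from 20 s to unable loses 4/20 = 0.2 stairs/s; slowing from 2.0 s to 2.5 s loses 4/2.0 − 4/2.5 = 0.4. Losing the ability would score as the milder change.

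**Conclusion.** The point holds for the Part 2 TA 4-stair ascent and descent analyses. The SAP separates inability from a test not done, then gives inability no value in the endpoint it tests. Followed as written, and on the inference that the time is blank, becoming unable is scored as a finite time in the version labelled primary for this endpoint. That favours the arm losing function.

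The size cannot be computed from the documents. About 0.6 to 2 points on a 10-point effect is an illustration resting on a borrowed SD of 9%, 12 per arm, one earlier visit correlated 0.7 and 1 to 3 unable patients in one arm only. If nobody becomes unable, nothing changes. These are secondary motor-function endpoints; the total muscle volume analysis is untouched.

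**What to change.** In the SAP, for ascent and descent separately:
- Treat grade 1 at Day 190 as the worst outcome. Give it the tied worst rank in a rank-based comparison of change in time, stratified by or adjusted for MRC-MMT category.
- Count grade 1 at Day 190 as a non-responder in the 10% ascent criterion.
- Restrict missing-at-random imputation to grade 7 and other tests truly missing, and state how the rank test is pooled over the 20 imputations.
- Keep the percent-change-in-time ANCOVA for its effect estimate, labelled as conditional on being able to climb or descend.
- Add one sentence on a patient graded unable at every pre-dose visit; few or none are expected.

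The grades are already collected, so the cost is SAP wording and one further analysis before database lock. A rank test gives no effect estimate in percent, which is why the ANCOVA stays. In the illustration with nobody unable, the rank test rejected in 81.2% of runs against 83.7% for the t-test, so little power is given up.
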